The **1L Nivolumab vs Sorafenib Cohort** will consist of approximately 130 advanced HCC subjects who are naive to systemic therapy (uninfected, HCV-infected, or HBV-infected) who will be randomized 1:1 to receive open label flat dose nivolumab 240 mg Q2 week IV (Arm A) or sorafenib 400 mg po BID (Arm B) until unacceptable toxicity or RECIST 1.1 disease progression or study discontinuation for any other reason. Uninfected, HCV-infected, or HBV-infected subjects will be enrolled. Subjects will be stratified by viral status (HCV vs non-HCV [HBV infected or uninfected]) and presence of macrovascular invasion (MVI) or extrahepatic spread (EHS). Subjects with resolved HCV infection will be stratified into the HCV group.

The **Nivolumab and Ipilimumab Combination Cohort** will consist of up to 120 subjects. Uninfected, HCV-infected, or HBV-infected subjects with advanced HCC and previous treatment with sorafenib will be randomized 1:1:1 into 3 different dose arms:

- Arm A--nivolumab 1 mg/kg + ipilimumab 3 mg/kg q3 week x 4 followed by flat dose nivolumab 240 mg IV q2week until toxicity or disease progression (n = 40)
- Arm B--nivolumab 3 mg/kg + ipilimumab 1 mg/kg q3week x 4 followed by flat dose nivolumab 240 mg IV q2week until toxicity or disease progression (n = 40)
- Arm C--nivolumab 3 mg/kg q2week + ipilimumab 1 mg/kg q6week until toxicity or disease progression (n = 40).

A 2-stage design will be employed for each of the 3 dose arms. Twelve subjects in each dose arm will undergo a safety and tolerability assessment at Week 13 (or prior to Week 13 if discontinued). The safety evaluation (Section 3.1.4) will be conducted independently for each dose cohort based on criteria described in Discontinuation Criteria (Sections 4.1.18 for nivolumab and 4.2 for ipilimumab). No additional subjects will be enrolled until the safety evaluation at Week 13 occurs. After completion of Stage 1, enrollment in Stage 2 of the subsequent 28 subjects can occur in each dose arm and is contingent upon the results of the safety evaluation.

Tumor response will be evaluated using Response Evaluation Criteria in Solid Tumors (RECIST 1.1). It is recognized that there may be delayed responses following disease progression with nivolumab and other agents in this class. In these cases, subjects may continue treatment provided that they experience no clinical deterioration. These subjects will continue to be evaluated by RECIST 1.1.

Revised Protocol No.: 05

Date: 26-Oct-2016

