**Table 2: Observed ORR with Exact 95% CI and 90% Lower Bound**

Observed ORR	Exact 95% CI	90% Lower Bound
20%	(9.1%, 35.7%)	12.0%
25%	(12.7%, 41.2%)	16.2%
30%	(16.6%, 46.5%)	20.5%
35%	(20.6%, 51.7%)	24.9%
40%	(24.9%, 56.7%)	29.4%

**Primary Endpoint**Dose Escalation Phase

- The primary objective is safety and tolerability of nivolumab as evaluated by the following endpoints:
  - Incidence of adverse events (AEs), serious adverse events (SAEs), adverse events leading to discontinuation, and deaths.
  - Incidence of clinical laboratory test abnormalities.

Expansion Phase

- ORR, based on assessments by BICR under RECIST 1.1 criteria, is the primary endpoint. It is defined as the proportion of all treated subjects whose BOR is CR or PR. BOR is the best response designation per subject over the study prior to subsequent anti-cancer therapy. For a BOR of CR or PR, the initial response assessment must have been confirmed by a consecutive assessment no less than 4 weeks (28 days) later.

1L Nivolumab vs Sorafenib Cohort

- ORR, based on Investigator assessments under RECIST 1.1 criteria, is the primary endpoint. It is defined as the proportion of all randomized subjects whose BOR is CR or PR. For a BOR of CR or PR, the initial response assessment must have been confirmed by a consecutive assessment no less than 4 weeks (28 days) later.

Nivolumab plus Ipilimumab Combination Cohort

- The primary objective is safety and tolerability of nivolumab plus ipilimumab as evaluated by the following endpoints:
  - Incidence of adverse events (AEs), serious adverse events (SAEs), adverse events leading to discontinuation, and deaths.
  - Incidence of clinical laboratory test abnormalities.
- ORR, as assessed by Investigator under RECIST 1.1 criteria, is the co-primary endpoint. It is defined as the proportion of all treated subjects whose BOR is CR or PR. For a BOR of CR or PR, the initial response assessment must have been confirmed by a consecutive assessment no less than 4 weeks (28 days) later.

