### ***1.1.9 Rationale for Objective Response Rate as Primary Endpoint in 1L Sorafenib vs Nivolumab Cohort and Nivolumab plus Ipilimumab Combination Cohort***

As outlined in [Section 1.4.6](#), the response rate for nivolumab in predominantly 2L advanced HCC subjects of 19% (8 of 42 subjects) in the Dose Escalation Phase of CA209040 and preliminary 1 year survival of 61% compares favorably to sorafenib in the 1L setting as outlined in [Section 1.1.5](#) Antitumor activity has been observed in uninfected and viral-infected subjects, and at dose levels ranging from 0.1 mg/kg to 10 mg/kg. Overall, responses as assessed by RECIST1.1 have been observed in 8 of 42 subjects (19%) with evaluable response data, including 2 CRs and 6 PRs. In addition to preliminary anti-tumor activity, nivolumab has demonstrated an acceptable safety profile for subjects with advanced HCC (Section 1.4.6).

Objective Response Rate (ORR) as estimated by RECIST 1.1 assessments from a blinded independent central review (BICR) is the primary endpoint for the randomized [1L Nivolumab vs Sorafenib Cohort](#) and the [Nivolumab plus Ipilimumab Combination Cohort](#).

The primary analysis of ORR will be performed at least 6 months after the last patient first dose date. Six months follow-up is thought to be sufficient to characterize durable clinical benefit because in the dose escalation cohorts of CA209040, the majority of responses to nivolumab occurred early (by Week 12) in 7 of 8 subjects; the median duration of response (DOR) was approximately 12 months; and in 1L trials with sorafenib the median time to progression is usually < 4 months. This will allow sufficient follow up for ORR to have a stable estimate, adequate safety follow up, as well as information on duration of response in the [1L Nivolumab vs Sorafenib Cohort](#) and [Nivolumab plus Ipilimumab Combination Cohort](#). Furthermore, in advanced HCC subjects who received a systemic multikinase inhibitor, brivanib (BRISK-PS), ORR has been shown to be an independent predictor of OS with median OS of 16.4 months in brivanib responders vs 8.3 months for brivanib non-responders (hazard ratio 0.28; 95% CI 0.14 - 0.55, P < 0.01).

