#### **Treatment Phase:**

Nivolumab monotherapy will be given on an every two week schedule and one treatment cycle (42 days) is comprised of three doses in the Dose Escalation (at doses of 0.1 mg/kg to 10 mg/kg q2week) and Expansion Phase (3 mg/kg q2week). In the 1L Nivolumab vs Sorafenib Cohort, nivolumab monotherapy (240 mg IV) will be given on an every two week schedule with 1 dose = 1 cycle; sorafenib will be given 400 mg po BID. In the Nivolumab plus Ipilimumab Combination Cohort, the dosing will be as outlined above, with no less than 19 days between doses in Arms A and B during the q3week induction phase. In arm C, nivolumab doses may be given no less than 12 days between doses, and ipilimumab doses no less than 5 weeks between scheduled doses

All subjects except those in the 1L Nivolumab vs Sorafenib Cohort will undergo tumor assessments at every q6 week ( $\pm$  2 days) for the first 48 weeks, and then q12 week ( $\pm$  1 week) thereafter until disease progression. Subjects in 1L Nivolumab vs Sorafenib Cohort will undergo tumor assessments q8 week ( $\pm$  1 week) for the first 48 weeks, and then q12week ( $\pm$  1 week) thereafter until disease progression or treatment is discontinued (whichever occurs later). Imaging assessments should be scheduled regardless of dose delay or missed doses in all cohorts.

Prior to activation of Amendment 8, subjects in the Dose Escalation Phase were treated until either a confirmed CR, completion of 2 years of therapy, toxicity, or disease progression. However, upon activation of Amendment 8, all subjects are to be treated until toxicity, RECIST 1.1 defined progression ([Appendix 2](#)), unacceptable toxicity, or study discontinuation for any other reason ([Section 3.5](#)). Treatment may continue beyond progression under protocol defined.

Subjects will continue to receive nivolumab, sorafenib, or nivolumab plus ipilimumab until:

1. RECIST 1.1-defined radiographic progression or unacceptable toxicity.
2. Clinical deterioration ([Section 3.1.4](#)) suggesting that no further benefit from treatment is likely.
3. Meets criteria for discontinuation of study therapy as outlined in [Sections 3.1.3.1](#) (Dose Limiting Toxicity), [3.5](#) (Discontinuation of Subjects from Treatment), [4.1.18](#) (Nivolumab Permanent Discontinuation Criteria), [4.1.12](#) (Treatment Interruption or Discontinuation for Sorafenib Treatment) or [4.2](#) (Ipilimumab Permanent Discontinuation Criteria)

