#### **Follow Up Phase:**

Follow-Up Visit 1 to occur 35 days from the last dose ( $\pm$  7 days) or coinciding with the date of discontinuation of study drug ( $\pm$  7 days) if the date of discontinuation is greater than 42 days from the last dose. Follow-Up Visit 2 to occur 80 days from Follow-Up Visit 1 ( $\pm$  7 days).

Subjects who discontinue study drug for reasons other than radiographic progression or who continue treatment beyond progression will continue to have tumor assessments (if clinically feasible) according to the schedule in [Table 5.1-8](#) and [Table 5.1-9](#) and until progression or treatment discontinuation for subjects being treated beyond progression.

Subjects will be followed for drug-related toxicities until these toxicities resolve, return to baseline or are deemed irreversible. All adverse events will be documented for a minimum of 100 days after the last dose of study drug.

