### **3.1.8     *Treatment Beyond Progression for Nivolumab or Nivolumab plus Ipilimumab***

Accumulating clinical evidence indicates some subjects treated with immune system stimulating agents may develop disease progression by conventional response criteria before demonstrating clinical objective responses and/or stable disease. This phenomenon was observed in the Phase 1 study of nivolumab, CA209003, and confirmed in multiple Phase 3 studies (ie, lung CA209017; melanoma CA209037, CA209066, and CA209067). Two hypotheses explain this phenomenon. First, enhanced inflammation within tumors could lead to an increase in tumor size which would

appear as enlarged index lesions and as newly visible small non-index lesions. Over time, both the malignant and inflammatory portions of the mass may then decrease leading to overt signs of clinical improvement. Alternatively, in some individuals, the kinetics of tumor growth may initially outpace anti-tumor immune activity. With sufficient time, the anti-tumor activity will dominate and become clinically apparent. Therefore, subjects will be allowed to continue study therapy after an initial investigator-assessed RECIST 1.1 ([Appendix 2](#)) defined progression as long as they meet the following criteria:

- Investigator assessed clinical benefit
- Subject is tolerating nivolumab or nivolumab plus ipilimumab
- Treatment beyond progression will not delay an imminent intervention to prevent serious complications of disease progression (eg, CNS metastases)
- Subject provides written informed consent prior to receiving any additional nivolumab or nivolumab plus ipilimumab treatment, using an ICF describing any reasonably foreseeable risks or discomforts, or other alternative treatment options.

These criteria aim to ensure the risk/benefit for continuing treatment will continue to favor the subjects. The assessment of clinical benefit should take into account whether the subject is clinically deteriorating and unlikely to receive further benefit from continued treatment. The decision to continue treatment beyond initial investigator-assessed progression should be discussed with the BMS Medical Monitor and documented in the study records.

If the decision is taken to continue nivolumab treatment beyond progression, the subject will remain on the trial and continue to be treated and monitored according to the Time and Events Schedule in [Table 5.1-4](#), [Table 5.1-5](#) and, [Table 5.1-7](#).

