Subjects should discontinue study therapy upon further evidence of further progression, defined as an additional 10% or greater increase in tumor burden SLD from time of initial progression (including all target lesions and new measurable lesions). New lesions are considered measurable if the longest diameter is at least 10 mm (except for pathological lymph nodes, which must have a short axis of at least 15 mm). Any new lesion considered non-measurable may become measurable and therefore included in the tumor burden measurement if the longest diameter increases to at least 10 mm (except for pathological lymph nodes, which must have an increase in short axis to at least 15 mm). Nivolumab treatment should be discontinued permanently upon documentation of further progression.

For statistical analyses that include the investigator-assessed progression date, subjects who continue treatment beyond initial investigator-assessed, RECIST 1.1-defined progression will be considered to have investigator-assessed progressive disease at the time of the initial progression event.

For subjects discontinuing treatment because of global deterioration of health status without objective evidence of disease progression at that time, progression should be reported as “symptomatic deterioration”. Every effort should be made to document objective progression (ie, radiographic confirmation) even after discontinuation of treatment.

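### Expansion Phase primary ORR: the stated best-response window does not close at progression, so a confirmed response first seen after BICR progression can count

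*Combined protocol and SAP*

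**What the plan says.** **Endpoint.** The Synopsis (Primary Endpoint, Expansion Phase) defines the primary endpoint as ORR by BICR under RECIST 1.1, in all treated subjects. It gives the window as follows: "BOR is the best response designation per subject over the study prior to subsequent anti-cancer therapy". A CR or PR must be confirmed at the next assessment, at least 28 days later. Nothing requires that no progression came first.

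**Responses after progression are expected.** The Synopsis (Study Design) states: "It is recognized that there may be delayed responses following disease progression with nivolumab and other agents in this class". It adds that subjects who continue treatment in this situation go on being evaluated by RECIST 1.1. Section 3.1.8 gives the same rationale: some subjects "may develop disease progression by conventional response criteria before demonstrating clinical objective responses and/or stable disease".

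**Scanning continues.** If treatment goes on beyond progression, Section 3.1.8 says "the subject will remain on the trial and continue to be treated and monitored according to the Time and Events Schedule". Section 3.1.1 (Follow Up Phase) continues tumor assessments "until progression or treatment discontinuation for subjects being treated beyond progression".

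**The dating rule.** For analyses that use the investigator-assessed progression date, Section 3.1.8 says that subjects treated beyond progression "will be considered to have investigator-assessed progressive disease at the time of the initial progression event". It mentions neither BICR nor best overall response (BOR).

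**The concern.** The Synopsis states a window for this endpoint and gives it one end. A programmer who follows that sentence would include a confirmed response whose first scan comes after BICR progression, and the protocol supplies the route by which such a response could be seen and confirmed.

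The route is not limited to subjects whom the investigator knowingly treats beyond progression. Treatment and scanning follow the investigator's reading, while the endpoint follows BICR. If BICR dates progression earlier than the investigator does, later scans exist without any decision to continue past progression.

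The reported ORR could then merge two kinds of response under one number, with no instruction to separate them. It would also fit poorly with the quantities reported beside it. Duration of response belongs to the same primary objective, and time to progression and progression-free survival are secondary. A subject counted as a responder could already have had the progression event before the response began.

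**Working it through.** **1. Can the sequence occur on the schedule?** Section 3.1.1 (Treatment Phase) states: "All subjects except those in the 1L Nivolumab vs Sorafenib Cohort will undergo tumor assessments at every q6 week", with a window of 2 days either way, for the first 48 weeks. Take progression by BICR at Week 6, a first PR at Week 12 and a PR again at Week 18. The gap between the last two scans is nominally 42 days and at least 42 − 4 = 38 days. That exceeds 28 days, so the response is confirmed. If no subsequent anti-cancer therapy has started, every condition in the Synopsis sentence is met.

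**2. Does another visible rule exclude it?** The Section 3.1.8 dating rule, and its counterpart for sorafenib in Section 4.1.13, apply to investigator-assessed progression dates. The Expansion endpoint is BICR-assessed. Neither rule says that responses after the dated progression are left out of BOR.

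**3. Reproduce the plan's figure.** The Synopsis (Sample Size Determination) gives 10 responders among 50 subjects, 20%, with a 95% Clopper-Pearson lower bound of 10%. For x responders among n:

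- lower limit = the 0.025 quantile of Beta(x, n − x + 1)
- upper limit = the 0.975 quantile of Beta(x + 1, n − x)

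With x = 10 and n = 50, the limits are 10.03% and 33.72%. The stated 10% reproduces as the two-sided bound; a one-sided 95% bound would be 11.3%.

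**4. Sensitivity.** The documents give no count of responders whose first response follows BICR progression. Assume that 0 to 3 of the illustrative 10 are of this kind and are removed by a window that also closes at progression:

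| Removed | Responders/50 | ORR | 95% CI |
|---|---|---|---|
| 0 | 10 | 20% | 10.0% to 33.7% |
| 1 | 9 | 18% | 8.6% to 31.4% |
| 2 | 8 | 16% | 7.2% to 29.1% |
| 3 | 7 | 14% | 5.8% to 26.7% |

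Each subject moves ORR by 1/50 = 2 points. The lower bound moves by 10.03 − 8.58 = 1.45, then 8.58 − 7.17 = 1.41, then 7.17 − 5.82 = 1.35 points, or about 1.4 each.

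**5. What do the documents say about timing?** Only Section 1.1.9, on the Dose Escalation Phase: "the majority of responses to nivolumab occurred early (by Week 12) in 7 of 8 subjects". So 1 of 8 came later (12.5%, exact 95% CI 0.3% to 52.7%). This points to a small number but does not settle it. A late response need not follow progression, and step 1 shows that a Week 12 response can follow progression at Week 6.

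**The case against.** **The governing text may settle the point.** The Synopsis is a summary and refers to Section 8 for the full analyses. Section 8.3.1 and Appendix 2 (RECIST 1.1) were not available for this review, and no available text says whether BICR reads scans taken after progression. The endpoint is also tied to RECIST 1.1, which may be meant to carry a cut-off. This limit stands, and it is why the remedy is conditional. It does not remove the point: the Synopsis spells out its own window and confirmation rule, and it applies RECIST 1.1 evaluation to subjects already past progression.

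**The Synopsis may simply be abbreviated.** The first-line and combination cohorts have no BOR window in the Synopsis at all. A reader might infer that they share the defect. The documents do not support that: no window is stated for them that could be wrong, and their ORR is investigator-assessed. For them, a check of Section 8.3.1 is enough.

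**Late redefinition is a choice about what is estimated.** Section 3.1 closes Expansion enrollment on activation of Amendment 8, so narrowing the endpoint now is a late change, and a descriptive split alone would show the effect. This is fair as far as it goes. It is a reason to date the change openly, and the split is part of the fix. However, a split alone would leave the primary definition as it is. The narrower window can only lower the ORR or leave it unchanged, so it cannot favor nivolumab.

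**Conclusion.** The point holds for the Expansion Phase. On the Synopsis wording, a confirmed CR or PR first seen after BICR progression can count toward the primary ORR, and no available rule excludes it. Confidence is medium, because Section 8.3.1 and Appendix 2 could not be read.

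The size is 2 points of ORR and about 1.4 points of lower bound per such subject in a 50-subject arm. The range of 0 to 3 subjects is an assumption. If there are none, nothing changes.

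Two stronger readings are tempting and not supported:

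- **That the ORR will be inflated.** The documents show that such responses can count. They do not show that any occurred or that BICR reads the scans concerned.
- **That the result could fail to clear the historical sorafenib ORR of 2% to 7% cited in Section 1.1.3.** No available passage sets an ORR threshold, and the Expansion Phase is sized for estimation. The range is a first-line figure, whereas Section 3.3.1.1 requires prior sorafenib in three of the four Expansion cohorts and admits naive or intolerant subjects to the fourth. No stated decision turns on it.

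**What to change.** First check Section 8.3.1 and Appendix 2. If either already closes BOR at progression, align the Synopsis with it. Otherwise, put this in the Synopsis, and in Section 8.3.1 if it carries the same wording:

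> Expansion Phase BOR is the best response from first dose up to the first BICR-assessed RECIST 1.1 progression or the start of subsequent anti-cancer therapy, whichever is earlier.

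List responses first seen after BICR progression separately, as descriptive results. For the first-line and combination cohorts, check only that Section 8.3.1 states the matching window by investigator assessment.

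The cost is one sentence in a primary endpoint definition, dated by amendment, and one listing from scans that the protocol already schedules. No new visits or data are needed. The downside is that the reported ORR may be slightly lower.

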**Secondary Endpoints**

The secondary efficacy endpoints for assessing antitumor activities include objective response rate (ORR) (Dose Escalation Phase only), CR rate, disease control rate (DCR), duration of response (DOR), TTR (time to response), TTP (time to progression), TTP Rate and PFS (progression free survival), all of which are based on BICR or investigator assessed response evaluation according to RECIST 1.1. These endpoints, as well as OS (overall survival) and OSR (overall survival rate), will be applied to all cohorts for treatment groups either as randomized (in

1L Nivolumab vs Sorafenib Cohort) or as treated (for all other cohorts). Definitions of the above secondary efficacy endpoints are available in [Section 8.3.2](#).

The following pharmacokinetic parameters of nivolumab derived from serum concentration time profile of subjects in the dose escalation phase will be included for PK analysis: Cmax, Tmax, AUC(TAU), Ctrough, Ceoinf, AI\_Cmax, AI\_AUC, and Effective T-Half.

- Cmax: Maximum observed serum concentration
- Tmax: Time of maximum observed serum concentration
- AUC(TAU): Area under the serum concentration time curve in the dosing interval
- Ctrough: Serum concentration achieved at the end of dosing interval (trough concentration)
- Ceoinf: Serum concentration achieved at the end of the infusion
- AI\_Cmax: Cmax at Cycle 3/ Cmax at Cycle 1
- AI\_AUC: AUC(TAU) at Cycle 3/ AUC(TAU) at Cycle 1
- Effective T-Half will be calculated by using formula below for AI>1 with AI being AI\_AUC

$$\text{Effective T - HALF} = \frac{\tau \ln(2)}{\ln\left[\frac{AI}{AI-1}\right]}$$

The secondary endpoints (for Dose Escalation and Expansion Phase) to assess the immunogenicity of nivolumab are incidence of subject ADA status, which include baseline ADA-positive, ADA-positive, and ADA-negative. Definitions of ADA status are described in the SAP.

